1.1. Project Design

(Protocol Amendment #6). This is a Phase 1/2a, dose-escalation study of E6201, a dual MEK1 and FLT3 inhibitor, in subjects with advanced hematologic malignancies with documented FLT3 and/or Ras mutations. The Phase 1 portion of the study will be conducted as a safety run-in in up to 30 subjects to establish a recommended Phase 2 dose (RP2D). The Phase 2a portion of the study will evaluate three specific patient groups: Cohort 1 will enroll up to 26 patients with relapsed or refractory AML and confirmed FLT3 mutation (with or without a Ras mutation) without prior exposure to a FLT3 inhibitor, Cohort 2 will enroll up to 26 patients with relapsed or refractory AML and confirmed FLT3 mutation (with or without a Ras mutation) with prior exposure to a FLT3 inhibitor, and Cohort 3 will enroll up to 10 patients with relapsed or refractory AML with a confirmed Ras mutation and no FLT3 mutation. Cohorts 1 and 2 of the expansion phase will incorporate a Simon 2-stage optimal design. A total of up to N= 92 subjects will be enrolled in the study.

The accrual phase for the Phase 1 Safety Run-in portion is expected to be 24 – 27 months. The expected accrual for the Phase 2a Expansion portion is expected to be 12 months, for a total accrual period of 36 – 39 months. With the last subject followed for up to 6 months, a total study duration of 42 – 45 months is anticipated. The anticipated accrual rate for the Phase 2a portion is 4 – 6 subjects per month across all sites.

During the study, a Safety Review Committee (SRC), consisting of the actively recruiting investigators, the Medical Monitor and Boston Strategics will review data from each cohort on an ongoing basis.

Subjects who demonstrate clinical benefit (objective response or stable disease) will be allowed to continue therapy with E6201 until progression of disease, observation of unacceptable adverse events, intercurrent illness or changes in the patient's condition that prevents further study participation. Subjects will be instructed to contact their study doctor for ophthalmic evaluation should they experience disturbances in their vision.

Safety will be assessed through the monitoring of adverse events (AEs), clinical laboratory parameters (hematology and serum chemistry), vital sign measurements, ECGs and physical examinations. Adverse events will be classified according to the Medical Dictionary for Regulatory Affairs (MedDRA) and graded according to the National Cancer Institute Common Terminology Criteria for Adverse Events (NCI CTCAE) version 4.03.

Efficacy assessment for AML will be performed using a modification of the recommendations of the International Working Group (IWG) for Diagnosis, Standardization of Response Criteria, Treatment Outcomes, and Reporting Standards for Therapeutic Trials in Acute Myeloid Leukemia. Efficacy assessments for subjects with MDS or CMML will be performed using a modification of the IWG Response Criteria in Myelodysplasia.

Pharmacokinetic determinations of E6201 in plasma will be made. Levels of pERK, pFLT3, pAKT, FLT3 ITD allelic burden, FLT3 ligand and plasma inhibitory assay (PIA) for FLT3, will be measured in blood and/or bone marrow samples collected from each subject. Additional markers or mutation analysis will be undertaken, if needed. Details of the PK analysis will be outlined in a separate Pharmacokinetic Report Analysis Plan.

1.2. Objectives

1.2.1. Primary Objective

- Phase 1: To determine the safety and tolerability of E6201 in subjects with FLT3+ and/or Ras+ AML, MDS or CMML and to establish a recommended Phase 2 dose (RP2D)
- Phase 2a: To evaluate the overall response rates (ORR) in subjects who receive E6201 for the treatment of FLT3+ and/or Ras+ relapsed/refractory AML

1.2.2. Secondary Objectives

- To evaluate duration of response
- To evaluate progression-free survival (PFS)
- To evaluate overall survival (OS)
- To evaluate the pharmacokinetics (PK) of E6201
- To explore pharmacodynamic (PD) changes from baseline in signal transduction markers in blood or/and bone marrow: pERK, pFLT3 and pAKT
- To explore quantitative changes from baseline in FLT3 internal tandem duplication (FLT3 ITD), FLT3 tyrosine kinase domain (TKD) and Ras+ allelic burden, FLT3 ligand and plasma inhibitory assay (PIA) for FLT3, and evaluate the correlation between FLT3 and Ras+ allelic burden and objective response
- To determine the safety and tolerability of E6201 at the RP2D (Phase 2a)

1.3. Treatment(s)

1.3.1. Treatment Assignments

Phase 1 (Safety Run-In): Phase 1 (Safety Run-In): Following Screening, a total of up to 30 subjects in up to 5 dose cohorts will be enrolled to establish the RP2D. The safety run-in phase will be a standard 3+3 cohort design.

Dose Level 1: 240 mg/m² weekly Days 1, 8, 15 and 22, repeated every 28 days (=1 cycle)

Dose Level 2: 320 mg/m² weekly Days 1, 8, 15 and 22, repeated every 28 days

Dose Level 3: 160 mg/m² twice weekly Days 1, 4, 8, 11, 15, 18, 22 and 25, repeated every 28 days (=1 cycle)

Dose Level 4: 240 mg/m² twice weekly Days 1, 4, 8, 11, 15, 18, 22 and 25, repeated every 28 days (=1 cycle)

Dose Level 5: 320 mg/m² twice weekly Days 1, 4, 8, 11, 15, 18, 22 and 25, repeated every 28 days

Phase 2a (Expansion): Once the Phase 1 Safety Run-In portion of the study is complete and an RP2D is established, additional subjects will be enrolled into the Phase 2 Expansion portion in three cohorts. Cohort 1 will enroll up to 26 patients with relapsed or refractory AML and confirmed FLT3 mutation (with or without a Ras mutation) without prior exposure to a FLT3 inhibitor. Cohort 2 will enroll up to 26 patients with relapsed or refractory AML and confirmed FLT3 mutation (with or without a Ras mutation) with prior exposure to a FLT3 inhibitor. Cohort 3 will enroll up to 10 patients with relapsed or refractory AML with a confirmed Ras mutation and no FLT3 mutation. Cohorts 1 and 2 of the Expansion Phase will incorporate a Simon 2-stage optimal design. Subjects with AML enrolled in the Phase 1

portion of the study at the RP2D will count towards the Phase 2a accrual for the appropriate cohort.

1.3.2. Selection and Timing of Doses

Phase 1 (Safety Run-In):

In the first cohort, the dose of E6201 will be 240 mg/m², administered as an intravenous (IV) infusion over 2 hours once weekly (Dose Level 1), on Days 1, 8, 15 and 22 of a 28-day schedule (=1 cycle). A minimum of 3 subjects will be treated. If 1 of 3 subjects experiences DLT during Cycle 1, the cohort will be expanded to 6. If ≥ 2 of 6 subjects experiences DLT by Day 28, no dose escalation to Dose Level 2 will occur. However, if 0 of 3 or ≤ 1 of 6 subjects treated at Dose Level 1 experience DLT by Day 28, dose escalation will proceed to the next cohort, 320 mg/m² weekly (Dose Level 2), administered by IV infusion over 2 hours on Days 1, 8, 15 and 22 of a 28-day schedule. A minimum of 3 subjects will be treated at this dose level. If 1 of 3 subjects treated at Dose Level 2 experiences DLT during Cycle 1, the cohort will be expanded to 6 subjects. If ≥ 2 of 6 subjects experience DLT by Day 28, no further dose escalation will occur.

However, if 0 of 3 or ≤ 1 of 6 subjects treated at Dose Level 2 experience DLT by Day 28, dose escalation will proceed to the next dose cohort, 160 mg/m² administered as an IV infusion over 2 hours twice weekly (Dose Level 3), on Days 1, 4, 8, 11, 15, 18, 22 and 25 of a 28-day schedule (=1 cycle). A minimum of 3 subjects will be treated at this dose level. If 1 of 3 subjects treated at Dose Level 3 experiences DLT during Cycle 1, the cohort will be expanded to 6 subjects. If ≥ 2 of 6 subjects experience DLT by Day 28, no further dose escalation will occur.

However, if 0 of 3 or ≤ 1 of 6 subjects treated at Dose Level 3 experiences DLT by Day 28, dose escalation will proceed to the next dose cohort, 240 mg/m² administered as an IV infusion over 2 hours twice weekly (Dose Level 4), on Days 1, 4, 8, 11, 15, 18, 22 and 25 of a 28-day schedule. A minimum of 3 subjects will be treated at this dose level. If 1 of 3 subjects treated at Dose Level 4 experiences DLT during Cycle 1, the cohort will be expanded to 6 subjects. If ≥ 2 of 6 subjects experience DLT by Day 28, no further dose escalation will occur.

However, if 0 of 3 or ≤ 1 of 6 subjects treated at Dose Level 4 experiences DLT by Day 28, dose escalation will proceed to the next dose cohort, 320 mg/m² administered as an IV infusion over 2 hours twice weekly (Dose Level 5), on Days 1, 4, 8, 11, 15, 18, 22 and 25 of a 28-day schedule. A minimum of 3 subjects will be treated at this dose level. If 1 of 3 subjects treated at Dose Level 5 experiences DLT during Cycle 1, the cohort will be expanded to 6 subjects. If there are ≤ 1 of 6 subjects with DLT at Dose Level 5, this dose (320 mg/m² twice weekly) will be declared the MTD and RP2D. If, however, ≥ 2 of 6 subjects experiences DLT, then either 320 mg/m² weekly (Dose Level 2) or 240 mg/m² twice weekly (Dose Level 4) will be declared the MTD and RP2D based on additional factors (e.g., PK and PD parameters).

Dose-limiting toxicity will be defined as any one of the following events: prolonged myelosuppression (as defined by the National Cancer Institute [NCI] criteria specific for leukemia, i.e., marrow cellularity $< 5\%$ at ≥ 6 weeks from start of therapy without evidence of leukemia); \geq Grade 3 non-hematologic toxicity (excluding Grade 3 nausea, vomiting or diarrhea that is adequately controlled with supportive care and resolves to \leq Grade 2 within 48 hours, or Grade 3 electrolyte disturbances responsive to correction within 24 hours); \geq

Grade 3 liver function tests (LFTs) lasting > 7 days; treatment interruption > 14 days due to toxicity; or other important medical event.

Phase 2a (Expansion):

Subjects will be enrolled into the Phase 2 Expansion portion in three cohorts. Subjects will receive E6201 weekly or bi-weekly on a 28-day schedule, with the schedule and dose level established in the safety run-in portion of the study.

As of July 17, 2017, this study was terminated due to lack of sufficient efficacy in the Phase 1 dose escalation portion of the study. Therefore, the SAP will include patient listing data and dose cohort summary tables for the 28 patients enrolled in the study.

1.4. Procedures

1.4.1. Subject Identification

Once study eligibility has been determined, a subject will be enrolled into the study and will be assigned a sequential Subject Identification number within each participating site. The identification number will consist of a 2-digit site number, 1-digit cohort number, and a 2 digit subject number. The subject identification number will be assigned sequentially within the cohort. The cohort number will remain the same if a subject's dose is increased or decreased. If a subject is replaced, the identification number will not be reassigned.

1.4.2. Randomization

Not Applicable

1.4.3. Blinding/Unblinding

This is an unblinded study.

1.4.4. Replacement

Subjects who are screened but do not receive E6201, and subjects treated in Cycle 1 who complete < 75% of their prescribed study drug treatment or do not complete C1D28 evaluation due to progression of disease, withdrawal of consent or non-DLT adverse events, will be replaced.

1.4.5. Data Monitoring

Strategia Therapeutics is responsible for ensuring the proper conduct of the study with regard to ethics, protocol adherence, site procedures, integrity of the data, and applicable laws and/or regulations. At regular intervals during the study and following completion of the study, the sponsor's study monitors will contact the study site via visits to the site, telephone calls, and letters in order to review study progress, CRF completion and address any concerns or questions regarding the study conduct. During monitoring visits, the following aspects of study conduct will be carefully reviewed: informed consent of subjects, subject recruitment, subject compliance with the study procedures, source data verification, drug accountability,

use of concomitant therapy by subjects, AE and SAE documentation and reporting, and quality of data. Records pertaining to these aspects are expected to be kept current.

2. Statistical Analysis Considerations

2.1. Sample Size and Power

A total of up to 92 subjects will be enrolled in this study.

Phase 1 (Safety Run-In): The sample size reflects requirements associated with a 3+3 design. A total of 3 to 30 subjects are planned (3 to 6 subjects in each of 5 dose cohorts) with FLT3+ and/or Ras+ AML, MDS or CMML.

Phase 2a (Expansion):

Cohort 1: The statistical objective for Cohort 1 in the dose expansion portion of the study is evaluation of the objective response (OR) rate within 3 cycles of treatment with E6201 in patients with AML and FLT3 mutation, or FLT3 plus Ras mutations, without prior exposure to a FLT3 inhibitor. If there is at least 1 OR in the first 8 patients, 18 additional patients will be enrolled in Stage II, for a total of 26 evaluable patients. If there are at least 4 ORs in a total of N=26, the alternative hypothesis will be accepted. This design provides a type I error of 5% and power of 85% when the true OR rate is 25%.

Cohort 2: The statistical objective for Cohort 2 in the dose expansion portion of the study is evaluation of the objective response (OR) rate within 3 cycles of treatment with E6201 in patients with AML and FLT3 mutation, or FLT3 plus Ras mutations, with prior exposure to a FLT3 inhibitor. Based on Simon's 2-stage optimal design, eleven (11) patients will be enrolled in Stage I. If there are zero (0) ORs in these 11 patients, the cohort will be terminated. If there is at least 1 OR in the first 11 patients, 15 additional patients will be enrolled in Stage II, for a total of 26 patients. If there are at least 2 ORs in a total of N=26, the alternative hypothesis will be accepted. This design provides a type I error of 5% and power of 80% when the true OR rate is 15% or greater.

Cohort 3: We will evaluate the objective response (OR) rate within 3 cycles of treatment with E6201 in up to 10 patients with AML and Ras mutation but no mutation in FLT3. A response rate of 20% in this patient population is considered clinically meaningful.

2.2. Analysis Populations

The full analysis set (FAS) includes all subjects who are administered any fraction of a dose of study medication. For a particular measure, the per-protocol set (PPS) includes those subjects in the FAS who have had a valid baseline and one or more post-treatment assessments for that measure of interest.

The E6201 PK population consists of all subjects in the FAS who complete all PK assessments. The E6201 PD population consists of all subjects in the FAS who complete all PD assessments. Details of the analysis will be outlined in the Pharmacokinetic Report Analysis Plan.

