2.3.2. Missing Data Conventions

Unless otherwise specified, missing data will be considered missing and will not be imputed.

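### The PK and PD populations admit only subjects with every assessment complete, so one missed sample or an early stop discards all of a subject's usable PK or PD data

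*SAP*

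**What the plan says.** SAP section 2.2 builds three sets from the full analysis set (FAS), which takes in anyone given any study drug at all.

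- **PK:** "The E6201 PK population consists of all subjects in the FAS who complete all PK assessments".
- **PD:** "The E6201 PD population consists of all subjects in the FAS who complete all PD assessments".
- **Per-protocol set (PPS), used for efficacy:** FAS subjects "who have had a valid baseline and one or more post-treatment assessments for that measure of interest".

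The PK and PD definitions make no exception for partial profiles. The section then adds: "Details of the analysis will be outlined in the Pharmacokinetic Report Analysis Plan". Section 2.3.2 sets the default for gaps: "Unless otherwise specified, missing data will be considered missing and will not be imputed".

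Sections 2.4.7 and 3.3.3 send PK and PD results to a separate report by an outside laboratory. Section 3 presents listings on the FAS but exempts PK and PD data. Section 1.3.2 records that the study was terminated in Phase 1 with 28 patients enrolled.

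**The concern.** A set defined by completing everything conditions on staying under observation. In relapsed or refractory leukaemia, that is plausibly related to outcome. Section 1.4.4 itself foresees treated subjects who "do not complete C1D28 evaluation due to progression of disease, withdrawal of consent or non-DLT adverse events, will be replaced". Those who received drug remain in the FAS, but they leave the PK or PD set if any required sample is missing.

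The PD rule is especially demanding. Section 1.1 lists pERK, pFLT3, pAKT, FLT3 ITD allelic burden, FLT3 ligand and the plasma inhibitory assay, in blood and/or marrow. Read literally, a gap in one marker removes the subject from the analysis of all the others.

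At stake is the description of exposure and target inhibition by dose. In a study stopped for insufficient efficacy, this is part of the remaining evidence on why the drug did not work. A summary of completers could leave out the early progressors, who matter most to that question.

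**Working it through.** The SAP states no PK or PD sample size, completion rate or sampling schedule, so there is no figure to reproduce. The check compares the provisions and then shows how retention behaves under assumed rates.

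**1. The rules side by side**

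| Set | Baseline required | Post-dose data required | Judged per measure? |
|---|---|---|---|
| PPS | yes, valid | at least one | yes |
| PK | not stated | all | no |
| PD | not stated | all | no |

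The SAP gives no reason for the stricter rule. Section 2.3.2 imputes nothing by default, so an excluded subject is not brought back that way. The FAS listings do not cover PK or PD data, so this SAP does not undertake to show the excluded values.

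**2. Does exclusion follow outcome?**

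Section 1.4.4 names progression, withdrawal of consent and non-DLT adverse events as reasons for an incomplete Cycle 1. Two of the three reflect disease course or toxicity. Replacement restores the head count but not the composition: the replacement can enter the PK and PD sets while the replaced subject drops out of them.

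The link is not automatic. A subject who misses the Day 28 evaluation may already have given every PK sample if PK sampling ends early in the cycle.

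**3. How many might be lost (illustration)**

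Inputs from the SAP are 28 enrolled (section 1.3.2) and cohorts planned at 3 to 6 (section 2.1). The assumptions, which are not in the SAP, are that all 28 were dosed, that a share d of subjects is incomplete, and that subjects are independent.

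- Expected number kept = 28 × (1 − d)
- Chance that a cohort of n is kept whole = (1 − d)^n
- Chance that at most 1 of 3 is kept = d³ + 3(1 − d)d²

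| d | Kept of 28 | All of 3 kept | All of 6 kept | At most 1 of 3 kept |
|---|---|---|---|---|
| 10% | 25.2 | 72.9% | 53.1% | 2.8% |
| 30% | 19.6 | 34.3% | 11.8% | 21.6% |
| 50% | 14.0 | 12.5% | 1.6% | 50.0% |

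**4. Missed samples alone**

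Assume each of k samples is missed independently with probability m. The share kept is (1 − m)^k.

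| m | k | Share kept | Of 28 |
|---|---|---|---|
| 2% | 5 | 0.98^5 = 90.4% | 25.3 |
| 2% | 10 | 0.98^10 = 81.7% | 22.9 |
| 5% | 10 | 0.95^10 = 59.9% | 16.8 |
| 5% | 15 | 0.95^15 = 46.3% | 13.0 |

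Low miss rates per sample can therefore remove many subjects once every sample is required, even with no early stopping.

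**The case against.** The strongest reply is that the definitions have little work to do in this SAP. No table or listing in section 4 uses the PK or PD population. The analysis sits in a separate plan that is not at hand and could define the sets differently. The sampling schedule is not shown, so the loss from the PK set may be small. Cohorts of 3 may also overstate the fragility. With 28 subjects in at most five cohorts of at most 6, the smallest holds at least 28 − 4 × 6 = 4, unless replacements took a cohort above 6.

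Much of this stands, and it limits the size of the problem. It does not remove it. Section 2.2 defers the details of the analysis but fixes the populations itself. If the separate plan uses other sets, the two documents conflict and need reconciling.

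A reader might draw three stronger conclusions that the SAP does not support:

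- **That the rule distorts dose selection.** Section 1.3.2 cites PK and PD parameters only as examples of additional factors, in the single branch where 2 or more of 6 subjects have a DLT at Dose Level 5. The study has since been terminated, and nothing says that choice would have been confined to these populations.
- **That it biases a planned marker-response analysis.** Section 1.2.2 does list an aim to "evaluate the correlation between FLT3 and Ras+ allelic burden and objective response", but section 3.3.2 provides no secondary endpoint analysis. The correlation is affected only if the separate report performs it.
- **That the harm can be measured by the response rate among completers.** The SAP never estimates response in the PD set. If completion depended on response alone, marker distributions within responders and within non-responders, and the odds ratio between them, would be unchanged.

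Nor does the SAP show that the subjects lost would be those with the highest exposure.

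**Conclusion.** The point holds as one about the definitions. Both sets are restricted to completers, more strictly than the SAP's own per-measure rule and without a stated reason. They can select on progression and toxicity, and they discard valid samples. The exposed results are the PK and PD summaries by dose in the separate report.

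The size is unknown. The retention figures rest entirely on assumed completion rates and only show how fast small cohorts thin out. PK is probably less exposed than PD or marrow samples taken later, but that depends on a schedule not shown here. The conclusion also assumes that the separate plan adopts the section 2.2 sets as written.

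Severity is low to moderate. The study is closed, this SAP plans no secondary endpoint analysis, and no dose decision under it remains open.

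**What to change.** Redefine both populations in section 2.2:

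- **PK population:** FAS subjects with at least one evaluable post-dose concentration. Report each PK parameter for those with enough samples to derive it.
- **PD population, marker by marker:** FAS subjects with a baseline and at least one post-dose value for that marker.
- **Reporting:** show n for every parameter and time point, and give the number excluded, with reasons, by dose cohort.
- **Consistency:** carry the same definitions into the Pharmacokinetic Report Analysis Plan. Changing section 2.2 alone could leave the two plans in conflict.

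The cost is two redefined sentences in the SAP, a short reporting provision and a matching edit in the separate plan. No new data are needed. The downside is that n will vary by parameter and time point, so summaries at different times will not always describe the same subjects. Showing n makes that visible.

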2.2.1. Intent-to-Treat (ITT) Population

This population will not be used in the analysis.

2.2.2. Randomized Population

Since this is not a randomized study, there is no randomized population.

2.2.3. Per Protocol Population

All efficacy endpoints will be initially based on the subjects receiving any fraction of a dose of study medication and having at least one post-baseline value (PPS) for a particular efficacy endpoint. For each efficacy endpoint, an assessment for any subject may be performed at a time point deemed appropriate by the investigator.

2.2.4. Safety Population

All safety endpoints will be based on the FAS dataset.

2.2.5. Screen Failure Population

This population will not be used in the analysis.

